16.5. VITAL SIGNS AND OTHER CLINICAL STATUS MEASURES

Weight (kg) and height at screening (cm), as well as vital signs for sitting systolic blood pressure (mmHg), sitting diastolic blood pressure (mmHg), sitting heart rate (bpm), sitting respiratory rate (breaths/min), and temperature (°C) will be collected and listed. Summaries of heart rate, temperature, systolic blood pressure, and diastolic blood pressure will be based on markedly abnormal criteria defined below:

Table 1. Vital Signs and Abnormal Criteria

Vital Sign	Abnormal Criteria
Heart rate (bpm)	< 60 bpm > 100 bpm
Temperature (°C)	≤ 35 °C ≥ 38 °C
Systolic blood pressure (mmHg)	120-139 mmHg, inclusive (CTCAE grade 1) 140-159 mm Hg, inclusive (CTCAE grade 2) ≥ 160 mmHg (CTCAE Grade 3)
Diastolic blood pressure (mmHg)	80-89 mmHg, inclusive (CTCAE grade 1) 90-99 mm Hg, inclusive (CTCAE grade 2) ≥ 100 mmHg (CTCAE grade 3)

Incidence of abnormal worst-case values will be presented. For heart rate and temperature, both high and low values will be presented separately such that subjects can be counted in both categories. Abnormal vital sign values will be flagged as such on a vital sign listing.

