6.2.2. BASELINE ASSESSMENTS

Baseline data are defined as the last non-missing assessment (including unscheduled assessments) prior to starting treatment. If there is more than one value on or prior to starting treatment, the value closest to and prior to the receipt of the first dose, whether scheduled or unscheduled, will be used as the baseline value. Unless the collection time or label indicates otherwise, assessments performed on the same day as the first dose of study drug will be considered performed prior to the start of treatment. AEs and medications reported with a start date on the date of first dose will be considered to have occurred after the start of treatment. For vital signs (excluding weight and height) and ECG measures, baseline results will be identified for the set.

For laboratory parameters, the baseline time point will be determined separately for each parameter.

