11. DEMOGRAPHIC AND OTHER BASELINE CHARACTERISTICS

Demographic data and other baseline characteristics will be summarized by study part and overall, and listed for the Enrolled population. Demographics will include age (derived, in years), sex, race, ethnicity, and baseline characteristics will include, but not limited to, Eastern Cooperative Oncology Group (ECOG) performance status, complete physical examination, vital signs and drug/alcohol screening details.

Baseline disease characteristics will include tumor diagnosis (TD), prior anticancer therapy (yes/no), prior radiotherapy (yes/no), prior cancer related surgery (yes/no), progressive disease prior to study entry (yes/no), prior disease progression date of last progression prior to the study enrollment, blood smear (BS), Bone Marrow Aspirate/Biopsy (BM) and time from date of last disease progression to study entry (in months).

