16.2. LABORATORY EVALUATIONS

The specific hematology, chemistry, and urinalysis analytes collected for the study are described in Appendix 2 of the protocol. Summary tables and listings of local laboratory data will be represented in SI units, where applicable. Laboratory values that are reported as 'below the detectable limit' of an assay will be analyzed as half the detectable limit for quantitative analysis but listed as originally reported. The following summaries will be provided for laboratory data:

- Shift from baseline grade to worst post-baseline grade based on NCI CTCAE v5.0 (for analytes where CTCAE grading applies). A missing baseline grade will be assumed to be grade 0. For laboratory tests with both low and high values, summaries will be provided separately.
- Shift from baseline to worst post-baseline value that is $< 0.25 \times LLN$ or $> 2.5 \times ULN$ (for analytes not gradable by NCI CTCAE v5.0).

All lab data will be listed. An additional listing will be presented for subjects with a post-baseline analyte that is grade 3 or higher (per NCI CTCAE) or that is $< 0.25 \times LLN$ or $> 2.5 \times ULN$ (for analytes not gradable by NCI CTCAE). For the later listing, all values for that analyte will be listed.

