16.4. ECG EVALUATIONS

12-Lead echocardiogram (ECG) measures (singlets and triplicates) will be collected according to the schedule of events, which varies by study part. When triplicates are collected, the averages will be used in the summaries.

The investigator will provide an overall interpretation of the ECG (i.e. clinically significant, yes or no). For the Fridericia correction of QT interval for heart rate (QTcF), markedly abnormal criteria will be defined as described in the table below.

ECG values, the investigator's interpretation of the ECG, and other information collected will be listed. QTcF values meeting markedly abnormal criteria will be flagged.

The following tables will be provided for the QTcF:

- Quantitative 12-lead ECG measurements: Shift from baseline to worst post-baseline in QTcF status categorized as markedly abnormal or not (defined in the table below)
- Quantitative 12-lead ECG QTcF measurements: Counts and percentages of subjects whose worst-case changes from baseline in QTcF measurements meet markedly abnormal criteria (described in the table below for changes from baseline).

QTcF Measure	Markedly Abnormal Criteria
Observed Measures	450–480 msec, inclusive [CTCAE grade 1] 481–500 msec, inclusive [CTCAE grade 2] > 500 msec [CTCAE grade 3 or higher]
Observed Changes from Baseline	>30 msec increase from baseline >60 msec increase from baseline

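### SAP 16.5 counts worst-case vital signs, with blood pressure abnormal from 120/80 upward, without crossing them with baseline and without a low blood-pressure category

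*SAP*

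**What the plan says.** SAP 16.5 lists all vital signs and summarises heart rate, temperature, systolic and diastolic pressure against Table 1, which it describes as markedly abnormal criteria. The only summary named is "Incidence of abnormal worst-case values will be presented".

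- The lowest blood-pressure rows are "120-139 mmHg, inclusive (CTCAE grade 1") for systolic and "80-89 mmHg, inclusive (CTCAE grade 1") for diastolic. Two higher grades follow: 140–159 and ≥160 systolic, 90–99 and ≥100 diastolic.
- Low limits exist only for the other two signs: "For heart rate and temperature, both high and low values will be presented separately such that subjects can be counted in both categories".
- A baseline exists. SAP 6.2.2 says "For vital signs (excluding weight and height) and ECG measures, baseline results will be identified for the set", and SAP 11 includes vital signs among the baseline characteristics tabulated for the Enrolled population ("complete physical examination, vital signs and drug/alcohol screening details").
- Other safety measures are crossed with baseline. SAP 16.2 has "Shift from baseline grade to worst post-baseline grade based on NCI CTCAE v5.0" and SAP 16.4 has "Shift from baseline to worst post-baseline in QTcF status categorized as markedly abnormal or not", plus categories of change from baseline. SAP 16.3 summarises the ECOG shift to best and worst post-baseline value.

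SAP 6.2.3 lets unscheduled readings contribute to worst-case values. SAP 6.1 groups the tables by study part and overall.

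**The concern.** Vital signs, with blood pressure named, are a secondary safety endpoint in both parts (Protocol 6.1). A reader of the planned table will want to know whose readings moved after dosing. The table does not show this: a subject at 125/82 before dosing and throughout is counted in the same row as one who rose from 110/70 to 125/82. The baseline table in SAP 11 does not help, because two separate marginal tables cannot show which subjects changed.

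No eligibility criterion sets a numeric blood-pressure limit, so baseline values may be spread over several Table 1 categories. By contrast, QTcF is capped at 450 msec at entry and still gets a shift table.

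The blood-pressure rows are also one-sided. A fall in pressure is neither counted in the summary nor flagged in the listing, since the flag follows Table 1.

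**Working it through.** **Step 1. Sections side by side.**

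| Measure | SAP section | Crossed with baseline? | Worst value stated as post-baseline? | Low direction? |
|---|---|---|---|---|
| Laboratory grades | 16.2 | Yes | Yes | Yes, separately |
| ECOG | 16.3 | Yes | Yes | Not applicable |
| QTcF | 16.4 | Yes, plus change | Yes | No |
| Heart rate, temperature | 16.5 | No | Not stated | Yes |
| Blood pressure | 16.5 | No | Not stated | No |

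The plan states no figure for this outcome, so there is none to reproduce. The remaining steps ask how informative the any-abnormal count would be.

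**Step 2. Number of readings (Protocol Tables 3 and 4, clinic-visit footnotes).** Cycle 1 visit days after Day 1:
- Part 1: days 2–3 (2), 15–18 (4), 21–22 (2), 25/28/31/34 (4), 36–39 (4) = 16. With the end-of-study visit, k = 17.
- Part 2: days 2–3 (2), 15–17 (3), 19 and 21 (2), 24–26 (3) = 10. With the end-of-study visit, k = 11.

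These are minimum counts for subjects who complete Cycle 1.

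**Step 3. Share flagged with no drug effect.** The pressures are assumptions. Each subject has a true mean m, normal around μ with between-subject SD 15 mmHg, and each reading adds normal noise with SD 8. Then

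P(worst ≥ c) = 1 − ∫ Φ((c − m)/8)^k · φ(m; μ, 15) dm.

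With c = 120:

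| Assumed mean systolic | One baseline reading ≥120 | Worst ≥120, k = 11 | Worst ≥120, k = 17 |
|---|---|---|---|
| 105 | 19% | 44% | 48% |
| 110 | 28% | 57% | 61% |
| 115 | 38% | 69% | 72% |
| 120 | 50% | 79% | 82% |
| 125 | 62% | 87% | 89% |
| 130 | 72% | 93% | 94% |

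For diastolic pressure (c = 80, assumed SDs 9 and 6), the share for k = 11 to 17 is 28–33% at a mean of 65, 48–53% at 70, 68–73% at 75 and 84–87% at 80.

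A second systolic set (SDs 12 and 8, k = 10 and 16, cut at 119.5) gives 59–64% at a mean of 110 and 84–87% at 120.

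**Step 4. Early leavers.** The plan assumes about 40% drop-out, and early leavers have fewer readings. As an extreme bound, let that 40% contribute one reading each (Part 2 to Part 1):
- Mean 110: 0.6×0.57 + 0.4×0.28 = 0.45 to 0.6×0.61 + 0.4×0.28 = 0.48.
- Mean 115: 0.6×0.69 + 0.4×0.38 = 0.57 to 0.6×0.72 + 0.4×0.38 = 0.58.
- Mean 120: 0.6×0.79 + 0.4×0.50 = 0.67 to 0.6×0.82 + 0.4×0.50 = 0.69.

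**Step 5. What crossing with baseline adds (mean 120, k = 17; simulation of 100,000 subjects, SDs 15 and 8).** With no drug effect, the 82% flagged split into 50% already at or above 120 at baseline and 32% newly so. Comparing no effect with an assumed +10 mmHg:

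| Summary | No effect | +10 mmHg |
|---|---|---|
| Worst ≥120 | 82% | 94% |
| Worst ≥140 | 36% | 61% |
| Worst ≥160 | 5% | 16% |
| Up one or more categories | 57% | 86% |
| Up two or more categories | 4% | 22% |

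The any-abnormal row is near its ceiling, but the higher rows move. A one-category shift is common by chance because the worst of 17 readings is compared with one baseline. A two-category shift is not.

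**The case against.** The strongest reply is that this table is not the only safeguard.

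- **Adverse events.** Protocol 12.3.1 asks for clinically significant vital-sign changes to be reported as AEs. Protocol 12.4.1.4 sends vital signs that worsen from baseline, or that are clinically significant, to AE or SAE recording. SAP 16.1 tabulates treatment-emergent events by term, severity and relationship to each drug. A reader might infer that a hypotensive subject is counted nowhere. The documents do not support that: a clinically significant fall should appear in the AE tables. What stands is that the vital-sign summary omits it.
- **Graded categories.** A reader might infer that the table cannot show a drug effect. That is also too strong, because the ≥140 and ≥160 rows respond in Step 5. What stands is that no row separates pre-existing from new values.
- **Listings.** Every value is listed, and with about 40 subjects a reviewer can trace individuals. This helps, but it leaves to manual work what the SAP tabulates for its other safety measures.
- **Post-baseline.** This is the natural reading of worst-case, given SAP 16.2 to 16.4. The omission is a wording gap.
- **Scope.** Protocol 13.3 promises only a descriptive summary on marked abnormality criteria. No test or stopping rule depends on the table.
- **Limits of the remedy.** In an uncontrolled study a shift table does not isolate a drug effect, and by itself it does not separate tazemetostat alone from tazemetostat with itraconazole or rifampin. This is correct and limits what the fix can claim.

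**Conclusion.** The point holds as a reporting weakness in one descriptive secondary safety table. As written, SAP 16.5 mixes values present before dosing with those arising on treatment and has no place for low blood pressure, while laboratory grades, ECOG and QTcF are all compared with baseline.

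That the count would flag most subjects is conditional. It holds for completers if mean systolic pressure is about 110 mmHg or more (57–61% at 110, 79–82% at 120) and fails at 105 (44–48%). If early leavers contributed only one reading each, the mean would need to be nearer 115. All of this rests on assumed means and SDs that the documents do not give.

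The primary PK analysis is not affected. The change is worth making because it is cheap, not because a conclusion of the trial depends on it.

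**What to change.** In SAP 16.5:

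1. State that worst-case means worst post-baseline.
2. Replace or supplement the incidence table with a shift from baseline category to worst post-baseline category for systolic pressure, diastolic pressure, heart rate and temperature, with high and low directions shown separately.
3. Report blood-pressure shifts of two or more categories on their own line. Do not label one-category shifts treatment-emergent, since they are common by chance.
4. Add a low blood-pressure category, shown and flagged separately from the high ones, with a threshold chosen and justified by the sponsor.

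The cost is SAP wording and one table shell before database lock. The readings and the baseline definition already exist, and no visit or measurement is added.

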17. PHARMACOKINETIC AND PHARMACODYNAMIC ANALYSES

17.1. PHARMACOKINETIC (PK) ANALYSES

All pharmacokinetic analyses will be performed based on the PK population.

Plasma concentrations will be summarized using descriptive statistics (n, mean, standard deviation (SD), coefficient of variation (CV%), standard error (SE) of the mean, median, maximum, and minimum) at each scheduled evaluation time point. The mean PK concentrations will be plotted over time since last dose and time since first dose. PK concentration data will be listed.

All PK analyses will be described in a separate Pharmacokinetic Analysis Plan (PKAP). Results from PK analyses will be reported in a PK report, and the key messages will be summarized in the CSR, or in separate publications.

17.2. PHARMACODYNAMIC (PD) ANALYSES

No PD analysis will be performed.

18. REFERENCES

APPENDIX 1. PARTIAL AND MISSING DATES CONVENTIONS**ALGORITHM FOR TREATMENT EMERGENCE OF ADVERSE EVENTS****Table 2. Treatment-emergent Adverse Events**

START DATE	STOP DATE	ACTION
Known	Known/Partial/Missing	If start date < study drug start date, then not TEAE If start date >= study drug start date and < (end of treatment + 30 days) or start date of new anticancer therapy, whichever is sooner, then TEAE If start date > (end of treatment + 30 days) or start date of new anticancer therapy, whichever is sooner, then not TEAE
Partial, but known components show that it cannot be on or after study drug start date	Known/Partial/Missing	Not TEAE
Partial, could be on or after study drug start date	Known	If stop date < study drug start date, then not TEAE If stop date >= study drug start date, then TEAE
	Partial	Impute stop date as latest possible date (i.e. last day of month if day unknown or 31st December if day and month are unknown), then: If stop date < study drug start date, then not TEAE If stop date >= study drug start date, then TEAE
	Missing	Assumed TEAE
Missing	Known	If stop date < study drug start date, then not TEAE If stop date >= study drug start date, then TEAE
	Partial	Impute stop date as latest possible date (i.e. last day of month if day unknown or 31st December if day and month are unknown), then: If stop date < study drug start date, then not TEAE If stop date >= study drug start date, then TEAE
	Missing	Assumed TEAE

ALGORITHM FOR PRIOR AND CONCOMITANT MEDICATIONS**Table 3. Prior and Concomitant medications**

START DATE	STOP DATE	ACTION
Known	Known	
If stop date < study drug start date, assign as prior.
 
If stop date >= study drug start date & start date<=end of study treatment or discontinued date of study drug, assign as concomitant.
 
If stop date>=study drug start date & start date < study drug start date, assign as both prior and concomitant.

	Partial	
Impute stop date as latest possible date (i.e. last day of month if day unknown or 31st December if day and month are unknown), then:
 
If stop date < study drug start date, assign as prior.
 
If stop date >= study drug start date & start date<=end of study treatment or discontinued date of study drug, assign as concomitant.
 
If stop date>=study drug start date & start date < study drug start date, assign as both prior and concomitant.

	Missing	
If stop date is missing could never be assumed a prior medication.
 
If start date <=end of study treatment or discontinued date of study drug, assign as concomitant.

Partial	Known	
Impute start date as earliest possible date (i.e. first day of month if day unknown or 1st January if day and month are unknown), then:
 
If stop date < study drug start date, assign as prior.
 
If stop date >= study drug start date & start date<=end of study treatment or discontinued date of study drug, assign as concomitant.
 
If stop date>=study drug start date & start date < study drug start date, assign as both prior and concomitant.

	Partial	
Impute start date as earliest possible date (i.e. first day of month if day unknown or 1st January if day and month are unknown) and impute stop date as latest possible date (i.e. last day of month if day unknown or 31st December if day and month are unknown), then:
 
If stop date < study drug start date, assign as prior.
 
If stop date >= study drug start date & start date<=end of study treatment or discontinued date of study drug, assign as concomitant.
 
If stop date>=study drug start date & start date < study drug start date, assign as both prior and concomitant.

	Missing	
Impute start date as earliest possible date (i.e. first day of month if day unknown or 1st January if day and month are unknown), then:
 
If stop date is missing could never be assumed a prior medication.
 
If start date <=end of study treatment or discontinued date of study drug, assign as concomitant.

Missing	Known	
If stop date < study drug start date, assign as prior.
 
If stop date >= study drug start date, assign as concomitant.

START DATE	STOP DATE	ACTION

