Subjects may discontinue from the study after completion of Cycle 1 or can continue treatment (Cycle 2+ onwards) until Investigator-assessed clinical progression per standard practice, or unacceptable toxicity, or until another discontinuation criterion is met. For subjects continuing tazemetostat treatment at the recommended therapeutic dose (oral 800 mg tazemetostat twice daily [12 hours apart]), Cycle 2 will begin on day 40 (Cycle 2 Day 1) and each subsequent cycle from Cycle 2+ onwards will be of 28-day duration. Safety and tolerability will be assessed throughout the subject's participation. Subjects will be instructed to report any adverse events

that occur up to 30 days after the last dose of tazemetostat. Subjects must have an end of study visit 30 days after the last dose of tazemetostat for safety assessment.

Part 2: Tazemetostat and Rifampin Drug Interaction

Part 2 of the study will evaluate the drug-drug interaction between tazemetostat and rifampin in an open-label, fixed sequential cross over design (Figure 3).

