Subjects may discontinue from the study after completion of Cycle 1 or can continue treatment (Cycle 2+ onwards) until Investigator-assessed clinical progression per standard practice, or unacceptable toxicity, or until another discontinuation criterion is met. For subjects continuing tazemetostat treatment at the recommended therapeutic dose (800 mg tazemetostat twice daily [12 hours apart]), Cycle 2 will begin on day 27 (Cycle 2 Day 1) and each subsequent cycle from Cycle 2+ onwards will be of 28-day duration. Safety and tolerability will be assessed throughout the subject's participation. Subjects will be instructed to report any adverse events that occur up to 30 days after the last dose of tazemetostat. Subjects must have an end of study visit 30 days after the last dose of tazemetostat for safety assessment.

Figure 3: Study Schema (Part 2: Tazemetostat and Rifampin)

Part 2: DDI study of tazemetostat (800 mg) + rifampin (600 mg)

NOTE:

- Cycle 1 finishes on day 26 and cycle 2 begins on day 27 (Cycle 2 Day 1). Cycle 2 day 1 will begin on day 27 (+ 3 days). Tazemetostat dosing for Cycle 2+ will begin on day 1.
- PK blood samples will be collected pre-dose (0 hour), 0.5, 1, 1.5, 2, 4, 6, 8, 12, 24, 36, and 48 hours post-dose (Day 1 – 3, Day 15 – 17, and Day 24 – 26).
- Sparse PK samples will be collected pre-dose (0 hour) and 2 hours post-dose on day 10 and 21.

Rollover Study

All subjects who receive the recommended therapeutic dose of 800 mg tazemetostat twice daily [12 hours apart] for 9 Cycles or longer, and are eligible to continue receiving tazemetostat, will transfer to a Rollover Study CCI for monitoring and continued study drug at the Investigator and Medical Monitor's discretion.

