16.1. ADVERSE EVENTS

AEs will be coded using MedDRA v23.1. Summary tables will be based on treatment emergent adverse events (TEAEs) which are defined as AEs that started or worsened in severity on or after the day of the first dose of study drug through 30 days after the end of study drug or the initiation of subsequent anticancer therapy, whichever is earlier. All AEs, treatment emergent or otherwise, will be presented in AE listings.

Each summary table will include the incidence (number and percentage) of subjects reporting any TEAE, as well as, by SOC and PT. A subject will be counted only once with an SOC, even if the subject experienced more than one TEAEs within that specific SOC (likewise for PT).

Investigator assessed severity grade will be based on the National Cancer Institute CTCAE v5.0. A subject will be counted only once with the worst severity grade within a SOC and/or PT.

Investigator assessed causality to study drug will be categorized as “not related,” “unlikely related,” “possibly related,” or “probably related” to study drug. For summary purposes, treatment-related TEAEs will include events with relationship to study drug classified as “not related” including both “not related” and “unlikely related” or “related” involving both “possibly related” and “probably related”. A TEAE with a missing causality will be classified as “related” to study drug. A subject will be counted only once at the strongest causality within a SOC and/or PT (related over not related).

TEAEs of special interest are defined in Section 12.4.2 of the protocol.

In accordance with the TEAE table presentation described above, AEs will be summarized as follows:

- TEAEs
- TEAEs of grade 3 or 4
- Treatment-related TEAEs
- Treatment-related TEAEs of grade 3 or 4
- TEAEs leading to dose interruption
- TEAEs leading to dose reduction
- TEAEs leading to discontinuation of study drug
- Serious adverse events (SAEs)
- Treatment-related SAEs

-
- TEAEs leading to death
 - TEAEs of special interest

For treatment-related summaries, relationship will be summarized by each study drug (Part 1: tazemetostat or itraconazole; Part 2: tazemetostat or rifampin).

Separate listings of SAEs, TEAEs leading to discontinuation of study drug, TEAEs leading to dose modifications, and TEAEs with an outcome of death will be provided. A listing of TEAEs of special interest will also be provided.

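### The date rule for treatment-emergent adverse events leaves a known onset exactly on the 30-day (or new-therapy) cutoff unclassified, in conflict with SAP 16.1

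*SAP*

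**What the plan says.** SAP 16.1 bases the adverse event summary tables on treatment-emergent events. The window for these opens on the day of first dose and runs "through 30 days after the end of study drug or the initiation of subsequent anticancer therapy, whichever is earlier". Read plainly, this includes day 30.

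SAP Appendix 1, Table 2 turns the definition into a date algorithm. Its first row covers events whose start date is known, and after excluding onsets before first dose it gives two rules:

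- Treatment-emergent: "If start date >= study drug start date and < (end of treatment + 30 days) or start date of new anticancer therapy, whichever is sooner".
- Not treatment-emergent: "If start date > (end of treatment + 30 days) or start date of new anticancer therapy, whichever is sooner, then not TEAE".

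The upper bound of the first rule, "and < (end of treatment + 30 days"), is strict, and so is the bound of the second. The row has no other rule. Table 2 does not say which drug's last dose marks end of treatment.

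On timing, Protocol 7.1 states: "Subjects must have an end of study visit 30 days after the last dose of tazemetostat". SAP 3.1 repeats this. The notes to Protocol Tables 3 and 4 add a window of ±3 days and move the visit forward if an investigational agent or cytotoxic chemotherapy starts first.

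**The concern.** A classification algorithm should give exactly one answer for every possible date. This one gives none on the cutoff day, where the SAP's own definition gives a clear yes. If the program follows Table 2 literally, a fully dated event on that day gets no treatment-emergent flag. Two programmers working independently could also resolve it differently, one from the appendix and one from 16.1.

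The day is not arbitrary. It falls in the window of the final safety visit, at which the schedules call for a complete physical examination, vital signs, ECG, laboratory tests and ECOG status. At stake is whether an event that 16.1 counts reaches the summary tables built on the flag.

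**Working it through.** The plan states no figure to reproduce. The check applies both rules as written, day by day.

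**Inputs**

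- Cutoff C = the sooner of (end of treatment + 30) and the start of new anticancer therapy (SAP Table 2 and 16.1).
- Table 2, known start date s on or after first dose: treatment-emergent if s < C; not if s > C.
- SAP 16.1: treatment-emergent if s <= C.
- Last Cycle 1 doses (Protocol 7.3): Part 1, tazemetostat day 36 and itraconazole day 38; Part 2, tazemetostat day 24 and rifampin day 25.
- Visit window: last tazemetostat dose + 27 to + 33 days.

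**Around the cutoff, no new therapy**

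| Onset relative to end of treatment | Table 2 | SAP 16.1 |
|---|---|---|
| +29 | treatment-emergent | treatment-emergent |
| +30 | no rule applies | treatment-emergent |
| +31 | not treatment-emergent | not treatment-emergent |

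**Where the gap falls against the visit**

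| Case | Nominal visit (window) | Gap if end of treatment = last tazemetostat dose | Gap if = last dose of any study drug |
|---|---|---|---|
| Part 1, stops after Cycle 1 | 36 + 30 = day 66 (63–69) | day 66 | 38 + 30 = day 68 |
| Part 2, stops after Cycle 1 | 24 + 30 = day 54 (51–57) | day 54 | 25 + 30 = day 55 |
| Part 1, last dose on day 67 (end of Cycle 2) | 67 + 30 = day 97 (94–100) | day 97 | day 97 |

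Under either reading of end of treatment, the unclassified day lies inside the visit window. It equals the nominal visit day in every case only if end of treatment means the last tazemetostat dose. Otherwise it differs by 2 days in Part 1 and 1 day in Part 2 for subjects who stop after Cycle 1.

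**New-therapy cutoff.** Suppose, for illustration, the last dose is on day 36 and new therapy starts on day 50. Then C = min(66, 50) = 50. Table 2 gives treatment-emergent on day 49, no rule on day 50, and not treatment-emergent on day 51. The same gap opens at this cutoff.

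**With <= in the treatment-emergent rule.** Onset at C becomes treatment-emergent, as in 16.1. Onsets at +29 and +31 keep their classification, and no known start date is left without one.

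**The case against.** The strongest reply is that the SAP already settles the matter. Section 16.1 is the definition and includes day 30. Appendix 1 is headed as a convention for partial and missing dates, and SAP 6.2.6 invokes it for imputation, so a fully dated event need never reach it. In part this stands: the intended answer can be inferred from 16.1, and the mismatch is probably a drafting slip. It does not remove the conflict, because the row in question is expressly for known start dates and gives an operational rule that differs from 16.1.

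A reader might go further and make three inferences that the documents do not support:

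- *Onsets pile up on the visit day.* Protocol 12.6 has the investigator record the date and time of onset, not of discovery, and symptoms raised at a visit will often have begun earlier. Under Protocol 12.4.1.3 a laboratory finding is an adverse event only if it is clinically significant and needs intervention or comes with symptoms. Some findings first seen at the visit may carry its date, but the documents give no rate.
- *The affected number can be computed.* Spreading 40 enrolled subjects evenly over the seven-day window gives 40/7 = 5.7, but this counts visits, not events. It also assumes that all 40 attend. Visits move forward when a new agent starts, and Protocol 5.5.1 reports that 144 of 895 subjects (16%) in the wider programme died within 30 days of last dose.
- *Events drop out of the report.* SAP 16.1 lists all adverse events, treatment-emergent or not. An unflagged event could be missed in the summaries but would remain in the listings, and it is missed only if the appendix is programmed literally and nobody queries the blank flag.

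**Conclusion.** Table 2 is wrong as written. For known start dates it leaves the cutoff day unclassified, whether the cutoff is 30 days after end of treatment or the start of new anticancer therapy, and this conflicts with SAP 16.1. That rests on the text alone and needs no assumption beyond reading 16.1 as inclusive.

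The size is one calendar day per subject. That day is inside the end-of-study visit window under both readings of end of treatment, but its match to the nominal visit day depends on an undefined term. The number of affected events cannot be estimated from the documents and is likely small. No data are lost. This is a minor correction, worth making because it costs almost nothing and removes a contradiction between a definition and its algorithm.

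**What to change.** Before database lock:

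1. In the known-start-date row of SAP Table 2, replace < with <= in the treatment-emergent rule. This matches 16.1 and also settles the start day of new anticancer therapy as inside the window.
2. Define end of treatment in Table 2 as the same last-dose date that 16.1 uses, and say in both places whether that is the last dose of tazemetostat or of any study drug.

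Optionally, add an upper bound for partial start dates whose known components place them after the cutoff; those rows currently have none. The correction does not depend on this.

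The two required changes cost one character, a defining sentence and the matching line in the program. They need no new data and no change to trial conduct.
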